capsules. Three RPC1063 dosage strengths have been prepared for the clinical investigations; 0.25 mg capsule), 0.50 mg (capsule), and 1.0 mg capsule).

For placebo, the same capsules will contain the same blended excipients described above. All three doses of RPC1063 and placebo capsules are identical in appearance.

Study treatment IFN β -1a and matching placebo injections will be supplied in prefilled syringes, which will be dispensed to patients at each visit and will contain a sufficient supply of IFN β -1a (or matching placebo) for each dosing interval.

DURATION OF TREATMENT:

Part A double-blind period: 24 weeks

Part A optional blinded extension period: At least 48 weeks.

Part B: 24 months (patients participating in Part A will not participate in Part B)

STUDY EVALUATIONS:

Primary Efficacy Endpoint:

Part A: Total number of GdE lesions, assessed on brain MRIs from Week 12 to Week 24

Part B: ARR at the end of Month 24

Secondary Efficacy Endpoints:

Part A:

Key Secondary Endpoints (rank ordered):

- The number of GdE lesions at Week 24
- Total number of new or enlarging hyperintense T2-weighted brain MRI lesions from Week 12 to Week 24
- ARR at the end of Week 24

Part B:

Key Secondary Endpoints (rank ordered):

CONFIDENTIAL

The information contained herein may not be used, disclosed, or published without the written consent of Receptos.

- The number of new or enlarging hyperintense T2-weighted brain MRI lesions over 24 months
- The number of GdE brain MRI lesions at Month 24
- Time to onset of disability progression as defined by a sustained worsening in EDSS of 1.0 points or more, confirmed after 3 months and after 6 months

Other Secondary Efficacy Endpoints

- Proportion of patients who are GdE lesion-free at Month 24
- Proportion of patients who are new or enlarging T2 lesion-free at Month 24
- The percent change in normalized brain volume (atrophy) on brain MRI scans from baseline to Month 24
- Change in MSFC score from Baseline to Month 24 (including the Low-Contrast Letter Acuity Test [LCLA] measurement of visual function as a component)
- Change in MSQOL-54 score from Baseline to Month 24

Exploratory Endpoints:

Part A:

[REDACTED]

Part B:

[REDACTED]

Safety (Secondary) Endpoints:

Part A

Cardiac safety and tolerability during initial dose titration will be evaluated in Part A patients according to the following monitoring schedule:

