The key secondary endpoints of cumulative number of new or enlarging T2 lesions between baseline and Month 24 and the number of GdE lesions at Month 24 will be analyzed using a negative binomial regression model with factors for treatment, region, age, and number of GdE lesions at baseline. The key secondary endpoint of time to onset of disability progression will be compared between treatment groups using Kaplan-Meier estimation and a Cox proportional-hazards model adjusted for region, age, and

CONFIDENTIAL

The information contained herein may not be used, disclosed, or published without the written consent of Receptos.

baseline EDSS score. Disability progressions confirmed at 3 months and at 6 months will be analyzed separately.

All safety data will be listed and summarized by treatment group. All treatment-emergent AEs will be coded and tabulated by system organ class and preferred term. Incidence of AEs, SAEs, and AEs leading to discontinuation will be summarized and presented in descending order of frequency. Associated laboratory parameters such as hepatic enzymes, renal function, and hematology values will be grouped and presented together. Individual patient values will be listed and values outside of the standard reference range will be flagged. Shift tables and analyses of changes from Baseline will be produced. The change from Baseline for each of the vital signs and ECG parameters will be summarized. Incidence of abnormal vital signs parameters and outlier ECG results will be tabulated.

Sample Size Justification:

The control ARR is assumed to be equal to 0.3 (Mikol, 2008). Assuming extra-Poisson variation ($\sigma^2=1.3$) (Polman, 2011) and 24 months of follow-up per patient, a total sample size of 999 patients (333 per arm) is estimated to provide 90% power to detect a 37% reduction in the ARR (i.e., an ARR of 0.19 for RPC1063) (Nicholas, 2011). In order to account for an assumed dropout rate of 17%, approximately 1200 patients (400 per arm) will be enrolled.

DATE AND VERSION: 01 October 2014 (Final Version 4.0)

CELGENE PROPRIETARY INFORMATION

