8.1.2. Secondary Study Objectives

Part A

- To assess the proportion of patients who are free of GdE lesions at Week 24
- To assess the effect of RPC1063 on the cumulative number of new/enlarging T2 lesions from Week 12 to Week 24
- To compare the clinical efficacy of RPC1063 to placebo in patients with RMS as assessed by reduction in annualized relapse rate (ARR) and proportion of relapse free patients at Week 24
- To assess the safety and tolerability of RPC1063 in patients with RMS
- To assess the pharmacokinetics (PK) and PD of RPC1063 in patients with RMS

Part B

- To assess the effect of RPC1063 on the proportion of patients with new/enlarging T2 lesions at Month 24
- To evaluate whether the efficacy of RPC1063 is superior to IFN β -1a in delaying the accumulation of disability, as assessed by the Multiple Sclerosis Functional Composite (MSFC), and visual function as measured by the low contrast visual acuity test (LCLA) (Balcer, 2000).
- To evaluate whether the efficacy of RPC1063 is superior to IFN β -1a in delaying the accumulation of disability, as assessed by the Expanded Disability Status Scale (EDSS)
- To assess the effect of RPC1063 on brain atrophy over 24 months
- To evaluate the effect of RPC1063 on patient-reported quality of life as assessed by the Multiple Sclerosis Quality of Life-54 (MSQOL-54)
- To assess the safety and tolerability of RPC1063 in patients with RMS

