8.2. Endpoints

8.2.1. Efficacy Endpoints

Part A

Primary Efficacy Endpoint:

- Total number of GdE lesions, assessed on brain MRIs from Week 12 to Week 24

Key Secondary Efficacy Endpoints (rank ordered):

- The number of GdE lesions at Week 24
- Total number of new or enlarging hyperintense T2-weighted brain MRI lesions from Week 12 to Week 24
- ARR at the end of Week 24

Exploratory Endpoints:

- [REDACTED]
- [REDACTED]
- [REDACTED]

Part B

Primary Efficacy Endpoint:

- ARR at the end of Month 24

Key Secondary Efficacy Endpoints (rank ordered):

- The number of new or enlarging hyperintense T2-weighted brain MRI lesions over 24 months
- The number of GdE brain MRI lesions at 24 months
- Time to onset of disability progression as defined by a sustained worsening in EDSS of 1.0 points or more, confirmed after 3 months and after 6 months

Other Secondary Efficacy Endpoints

- Proportion of patients who are GdE lesion-free at Month 24
- Proportion of patients who are new or enlarging T2 lesion-free at Month 24
- The percent change in normalized brain volume (atrophy) on brain MRI scans from baseline to 24 months
- Change in MSFC score from Baseline to Month 24 (including the Low-Contrast Letter Acuity Test [LCLA] measurement of visual function as a component)
- Change in MSQOL-54 score from Baseline to 24 months

Exploratory Endpoints:

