- 1 At Visit 1 an interim medical history will be performed to complete the screening medical history. Medical events that occur between screening and first dose will be recorded as medical history. All SAEs must be reported from the time of signing the informed consent; AEs are collected after the first dose.
- 2 Laboratory tests include Hematology, Chemistry, and Urinalysis.
- 3 Serum beta-hCG at screening, urine beta-hCG at each visit. If the urine pregnancy test is positive, do not dose and confirm with a serum pregnancy test.
- 4 Serology testing will be performed at screening to determine the patient's immune status with respect to the following viruses: Human immunodeficiency virus (HIV) antibodies, anti-hepatitis A virus IgM, hepatitis B surface antigen (HBsAg) and anti-hepatitis B core antigen (HBcAg) IgM, anti-hepatitis C virus (HCV) IgG or IgM. In addition, patients must have documentation of positive Varicella Zoster Virus (VZV) IgG antibody status or complete VZV vaccination at least 30 days prior to first dose of study medication.
- 5 The TB screening test (purified protein derivative) should be performed during the screening period and all testing must be completed prior to administration of study drug on Day 1. As available locally, an interferon gamma release assay such as QuantiFERON Gold test may be used as an alternative screening TB test or as a confirmatory test to rule out a false positive result using purified protein derivative.
- 6 Height at screening only.
- 7 A chest X-ray is not required if performed within 60 days prior to randomization and if documentation is on file.
- 8 Refer to [Table 5](#) for details of cardiac monitoring.
- 9 RPC1063 (0.5 or 1 mg) will be administered daily for the study duration; IFN β -1a 30 μ g will be administered by IM injection weekly.
- 10 Brain MRI scans will include a T2 and T1 scan (with and without Gadolinium) and will be performed at screening and then yearly.
- 11 Three MSFC practice assessments must be performed before baseline. These may be performed at the screening visit, or at any time between the screening and baseline visit.

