13.3. Statistical Analysis Plan

A Statistical Analysis Plan (SAP) will be written and finalized prior to any lock of the study database. The SAP will provide a detailed description of the statistical methods and expand on the details provided in the protocol. Additional analyses may be added. Tables, listing and figures shells will also be provided.

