The relapse rate will be based on only those relapses that were determined by the treating investigator to meet the protocol-defined definition of relapse, based on the EDSS scores obtained by the blinded evaluator (Section 9.1.2.3). New or recurrent neurological symptoms that occur less than 30 days following the onset of a protocol-defined relapse will be considered part of the same relapse, i.e., if 2 relapses have onset days that are ≤ 30 days of one another, they will be counted as 1 relapse (see Section 9.1.2.3).

The relapse rate for each treatment group will be calculated as:

$$(\text{total relapses in the arm}) / (\text{total days in the study for the arm}) * 365.25$$

The 3 key secondary endpoints will be tested in order in [redacted] ranking the RPC1063 1 mg dose above the RPC1063 0.5 mg dose. If both doses are significant on the primary endpoint, then the first comparison on the key secondary endpoints will be between the RPC1063 1 mg group and the IFN β -1a group at the 5% level of significance. If that comparison is successful, then the same endpoint will be tested for the RPC1063 0.5 mg group vs. the IFN β -1a group comparison at the 5% level of significance. This procedure will continue down the key secondary endpoint list until a comparison fails to reach statistical significance, [redacted]. If only 1 RPC1063 dose is significant on the primary endpoint, then the [redacted] will be employed on the surviving dose only, at the 2.5% level of significance for each key secondary endpoint.

The key secondary endpoints of cumulative number of new or enlarging T2 lesions between baseline and Month 12 and the number of GdE lesions at Month 12 will be analyzed using a negative binomial regression model with factors for treatment, region, age, and baseline number of GdE lesions. The key secondary endpoint of time to onset of disability progression will be compared between treatment groups using Kaplan-Meier estimation and a Cox proportional-hazards model adjusted for region, age, and baseline EDSS score. Results will be summarized by randomized treatment group and expressed as proportions, corresponding 95% confidence intervals, and p-values. Disability progressions confirmed at 3 months and at 6 months will be analyzed separately.

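### Protocol Section 13.6.4 analyses the first two ranked Part B key secondary endpoints at Month 12; the endpoint lists and the synopsis methods put both at Month 24

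*Protocol*

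**What the plan says.** Section 8.2.1 of the protocol ranks three key secondary endpoints for Part B. The first is "The number of new or enlarging hyperintense T2-weighted brain MRI lesions over 24 months". The second is the GdE lesion count at 24 months, which the synopsis list words as "The number of GdE brain MRI lesions at Month 24". The third is time to confirmed disability progression.

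The synopsis methods for Part B fit a negative binomial model, with treatment, region, age and baseline GdE count, to the "cumulative number of new or enlarging T2 lesions between baseline and Month 24 and the number of GdE lesions at Month 24". Section 13.6.4 repeats that sentence almost unchanged, with the same model and factors, but its outcomes are the "cumulative number of new or enlarging T2 lesions between baseline and Month 12 and the number of GdE lesions at Month 12".

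The paragraph before it in Section 13.6.4 sets the testing order, 1 mg ahead of 0.5 mg within each endpoint: "This procedure will continue down the key secondary endpoint list until a comparison fails to reach statistical significance". Each step is tested at 5% if both doses succeed on the primary endpoint. If only one does, that dose alone is tested at 2.5%.

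**The concern.** A confirmatory sequence needs one definition for each step. Here the first two steps have two written definitions, and data will exist for both. An analyst who works from Section 13, the natural source for a programming specification, would test a one-year T2 count and the Month 12 GdE scan. Neither is a declared key secondary endpoint.

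A failure at either step stops formal testing before disability progression is reached, so the choice of time point can decide whether that test takes place. Month 12 scans are also available a year before Month 24 scans. If the conflict is still open at unblinding, the protocol alone cannot show which time point was prespecified.

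**Working it through.** The point rests on comparing texts; the plan gives no figure of its own to reproduce.

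**Step 1: the time points side by side.**

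| Place in the protocol | New or enlarging T2 lesions (rank 1) | GdE lesions (rank 2) |
|---|---|---|
| Synopsis, ranked endpoint list | over 24 months | Month 24 |
| Section 8.2.1, ranked endpoint list | over 24 months | 24 months |
| Synopsis, Part B methods | baseline to Month 24 | Month 24 |
| Section 13.6.4, Part B | baseline to Month 12 | Month 12 |

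Three places say 24 months and one says 12. The T2 objective in Section 8.1.2 concerns the "proportion of patients with new/enlarging T2 lesions at Month 24". That is a proportion rather than the ranked count, so it supports the 24-month horizon only indirectly.

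**Step 2: can anything else explain Month 12?**
- The text is current protocol text, not an amendment log.
- The disputed sentence has no redaction, and both ranked lists are intact.
- Section 13.6.4 speaks of three key secondary endpoints, and neither list of three contains a Month 12 item.
- The MRI schedule does not decide between the two. Table 3, footnote 10, says scans "will be performed at screening and then yearly", and the visit sections list brain MRI at both Month 12 (10.3.6) and Month 24 (10.3.10).
- The SAP supplied covers Part A only. Its introduction defers Part B to a separate SAP.

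**Step 3: how much of the gated sequence is touched.** Count disability progression as one endpoint, as the protocol's count of three implies.
- Both doses succeed on the primary endpoint: 3 endpoints × 2 doses = 6 comparisons. Ranks 1 and 2 take 2 × 2 = 4, the first 4 of 6, each at 5%.
- One dose succeeds: 3 × 1 = 3 comparisons. Ranks 1 and 2 take 2, the first 2 of 3, each at 2.5%.

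**Step 4: what changes in each endpoint.**
- T2: 24 − 12 = 12 months of accrual are left out, half the declared window.
- GdE: the count comes from a single scan under either wording. No accrual is lost, but the Month 12 scan replaces the Month 24 scan.

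**Step 5: what cannot be computed, and what is not affected.** The documents give no Part B lesion rate or dispersion, so no change in power or error rate can be derived. The Part B sample size rests on the annualized relapse rate alone. With rates 0.30 and 0.19, variance factor 1.3, 2 years, two-sided alpha 0.025 and 90% power:

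n = (2.241 + 1.282)² × 1.3 × [1/(0.30 × 2) + 1/(0.19 × 2)] / [ln(0.19/0.30)]² = 332.4, or 333 per arm.

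This matches the stated 333, and the Month 12 or Month 24 question does not enter it.

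**The case against.** The best defence is that this is a clerical slip with a recoverable meaning. The gating paragraph runs down the key secondary list, that list says 24 months in both places, and the disputed sentence only assigns a model to endpoints defined elsewhere. The near-identical synopsis sentence reads Month 24. The separate Part B SAP may already say so too. Some text in the gating paragraph is redacted, so the procedure is not fully visible. The counts in Steps 3 and 4 describe scope, not a measured effect.

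Much of this stands. Month 24 is very probably what was intended, no wrong analysis has been shown to be under way, and no loss of power or error control is claimed. But a recoverable intention does not remove the contradiction. Section 13.3 makes the protocol the base for the SAP, which "will be written and finalized prior to any lock of the study database" and is to expand on the protocol's methods. A Part B SAP that is correct would still disagree with the protocol's own statistical section. Because both scans will exist, no missing data would expose the error.

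**Conclusion.** The concern holds and should be corrected before unblinding. Section 13.6.4 conflicts with the ranked lists in the synopsis and Section 8.2.1 and with the synopsis methods, on the time point of the two endpoints that stand ahead of disability progression. The scope is the first 4 of 6 gated comparisons, or the first 2 of 3, with progression counted as one endpoint. For T2, half of the declared window is at issue; for GdE, the choice of scan. The primary endpoint and the sample size are unaffected. Confidence in the contradiction is high. Its practical effect depends on the Part B SAP, which was not among the documents.

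A separate, lesser point at lower confidence: the Part A SAP, Section 9.2.1, describes the T2 endpoint as at Week 24, while its Sections 3, 4.2 and 9.2 define it from Week 12 to Week 24. This may be shorthand, since the 9.2.1 heading still speaks of a total number.

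**What to change.** In the Section 13.6.4 sentence that assigns the negative binomial model to the two lesion endpoints, replace both mentions of Month 12 with Month 24. State Month 24 for both endpoints in the Part B SAP before unblinding. If a Month 12 lesion analysis is wanted, label it supportive and keep it outside the gated sequence; resolving the conflict does not require one.

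The textual change is two words. Section 16.2 requires any protocol change to be handled as an amendment, so the cost is that process plus a consistency check of the Part B SAP. No data collection, visit or sample size changes.

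For the Part A point, restore the Week 12 to Week 24 window in the T2 heading and sentence of SAP Section 9.2.1. Add a rule for summing scans only if the reference scan for new or enlarging lesions is stated with it.

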13.4. Randomization

Patients will be randomized into the study on Day 1 using an IVRS provided by .

Part A

- Patients will be randomized 1:1:1 to receive placebo, 0.5 mg RPC1063, or 1 mg RPC1063. The randomization will be stratified by country.

Part B

- Patients will be randomized 1:1:1 to receive IFN β -1a 30 μ g, 0.5 mg RPC1063, or 1 mg RPC1063. The randomization will be stratified by baseline EDSS (≤ 3.5 , > 3.5) and country.

Treatment groups are described in [Section 9.5.1](#).

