13.6.4. Efficacy

Part A

For the primary analysis, the cumulative number of GdE lesions from Week 12 to Week 24 will be compared between the 1 mg RPC1063 group and the placebo group using the stratified Wilcoxon-Mann-Whitney test, stratified by presence of GdE lesions at baseline (absent or present). This comparison will be assessed using a 2-sided test at the $\alpha=0.04944$ level of significance (to keep the overall Part A level of significant at $\alpha=0.05$, accounting for the O'Brien-Fleming adjustment and interim analysis) (Reboussin, 2000). If the comparison between the 1 mg RPC1063 group and placebo is statistically significant, then a second primary analysis will similarly compare the 0.5 mg RPC1063 group and the placebo group, also based on a 2-sided test at the $\alpha=0.04944$ level of significance. Sensitivity and descriptive analyses will also be presented.

The secondary endpoint of the proportion of patients free of GdE lesions at Week 24 will be analyzed using a logistic regression model with treatment group (three levels) and presence of baseline GdE lesions (absent, present) as factors. Pairwise comparisons between the 1 mg RPC1063 group and placebo, and between the 0.5 mg RPC1063 group and placebo, will be tested.

Quantitative endpoints such as the percent brain volume change over 24 weeks will be analyzed using analysis of covariance models with treatment group as a factor and the baseline value of the corresponding parameter as a covariate.

Endpoints that are defined in terms of lesion counts will be analyzed using the Wilcoxon-Mann-Whitney test. These analyses will include only the two groups being compared.

All secondary endpoints will be analyzed using 2-sided tests at the 5% level of significance.

Part B

The primary analysis for the ARR will be carried out using a Poisson regression model. The model will compare treatment groups, adjusted for region, age, and the number of GdE lesions at baseline. To account for multiple comparisons, each of the 2 treatment comparisons with IFN β -1a will be tested at the $\alpha = 0.025$ level. Results will be summarized by randomized treatment group and expressed as unadjusted and adjusted relapse rates, odds ratios, corresponding 95% confidence intervals, and p-values.

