Other secondary endpoints that are defined as continuous variables will be analyzed using analysis of covariance models adjusted for region, age, and baseline measurements of the response parameter of interest. Other secondary endpoints defined as response proportions will be analyzed using a Cochran-Mantel-Haenszel test stratified by region and baseline EDSS category.

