### **Secondary Endpoint: The number of GdE lesions at Week 24**

The number of GdE lesions at Week 24 will be analyzed using the stratified Wilcoxon-Mann-Whitney test, stratified by presence of GdE lesions at baseline (absent or present). A sensitivity analysis will be using a negative binomial regression model, adjusted for the baseline number of GdE lesions. Missing GdE data values will be imputed using the mean from subjects of the same treatment group at the same visit.

The proportion of subjects who are GdE lesion free at Week 24 will be analyzed using Fisher's Exact test. Missing Week 24 GdE lesion data will be handled via LOCF. A sensitivity analysis will be conducted using the non-responder imputation method. For this analysis, any subject missing their Week 24 GdE lesion data will be counted as having 1 or more lesions at Week 24 (i.e., will be considered "not GdE lesion free" for this analysis).

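### The Part B lesion-free endpoints are tested without baseline GdE status, which forgoes a little precision if that baseline value is prognostic

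*Protocol*

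**What the plan says.** For Part B, protocol section 13.6.4 states: "Other secondary endpoints defined as response proportions will be analyzed using a Cochran-Mantel-Haenszel test stratified by region and baseline EDSS category". Section 8.2.1 lists two such proportions among the other secondary endpoints: "Proportion of patients who are GdE lesion-free at Month 24" and "Proportion of patients who are new or enlarging T2 lesion-free at Month 24".

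Elsewhere in 13.6.4, baseline GdE is used as follows:

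- Part B key secondary lesion counts (T2 and GdE): "negative binomial regression model with factors for treatment, region, age, and baseline number of GdE lesions".
- Part B primary relapse-rate model: "adjusted for region, age, and the number of GdE lesions at baseline".
- Part A proportion free of GdE lesions: "logistic regression model with treatment group (three levels) and presence of baseline GdE lesions (absent, present) as factors".

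The Part A SAP (section 9.2.1) handles that last endpoint differently: "The proportion of subjects who are GdE lesion free at Week 24 will be analyzed using" Fisher's exact test, with no baseline term.

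On allocation in Part B, section 13.4 says "The randomization will be stratified by baseline EDSS" (cut at 3.5) and country. Table 3 and its footnote 10 schedule a brain MRI with and without gadolinium at screening, so baseline GdE status is available before randomization. The Part A SAP (section 2) places the Part B analyses in a separate SAP, which is not among the documents.

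**The concern.** Whether a patient has enhancing lesions at baseline is the baseline value closest in kind to whether the patient has enhancing or new T2 lesions later. The sponsor treats it as worth adjusting for in the Part B lesion counts, and even in the relapse rate. The sentence just before the CMH rule adjusts continuous endpoints for their own baseline value. The lesion-free proportions, read from the same scans as the counts, are instead stratified by a disability category and not by GdE status. No reason is given.

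If baseline GdE is prognostic, leaving it out has two costs. The test has somewhat less power than the same data could give. A chance difference between arms in GdE-positive patients also stays in the comparison. Randomization does not balance this factor, and the entry criteria admit patients with or without a recent GdE lesion.

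**Working it through.** **1. The plan's own figure.** The documents give no power or sample size for the lesion-free endpoints, so the check uses the arm size planned for the relapse-rate comparison (protocol 13.2): control ARR 0.3, treated ARR 0.19, 24 months of follow-up, overdispersion 1.3, 90% power, alpha 0.025 (taken as two-sided).

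n per arm = (z₀.₉₈₇₅ + z₀.₉₀)² × 1.3 × [1/(0.3×2) + 1/(0.19×2)] / [ln(0.19/0.3)]²
= (2.241 + 1.282)² × 1.3 × (1.667 + 2.632) / 0.2086
= 332.4, rounded up to 333.

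This matches the plan. With 17% dropout, 333/0.83 = 401.2, in line with the stated 400 or so per arm.

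**2. Strata.** The documents do not define Part B regions. The Part A SAP uses three in its subgroup list. On that assumption the planned test has 3 × 2 = 6 strata, and adding baseline GdE (absent, present) gives 12. One dose against IFN is 2 × 333 = 666 patients, or about 55 per stratum on average.

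**3. Simulation.** Each scenario had 40,000 trials, 333 per arm, one dose against IFN, at two-sided 5%. The planned 6-stratum CMH test was compared with the 12-stratum version on the same simulated data. The documents supply none of the following, so all are assumptions:

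- baseline GdE present in 35% or 45% of patients;
- control lesion-free rate 65% or 80% for GdE, and 15% or 25% for T2;
- odds ratio for being lesion-free, baseline GdE absent versus present, from 1 to 5;
- region shares 20/10/70%, and EDSS above 3.5 in 15%;
- treatment effect tuned so that the planned test has about 80% power.

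| GdE absent/present odds ratio | Change in power from adding the stratum (points) |
|---|---|
| 1 (not prognostic) | -0.5 to -0.2 |
| 1.5 | -0.2 to 0.0 |
| 2 | +0.3 to +0.8 |
| 3 | +1.0 to +2.1 |
| 5 | +1.8 to +4.7 |

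The largest gain is for GdE-free with a 65% control rate, 45% GdE-positive at baseline and an odds ratio of 5, where power goes from 79.7% to 84.4%. The smallest gain at that odds ratio is for T2-free with a 15% control rate and 35% GdE-positive, from 79.4% to 81.2%. Relative efficiency over all scenarios runs from 0.99 to 1.13. The Monte Carlo standard error of one power estimate is √(0.8 × 0.2/40,000) = 0.2 points.

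**4. Validity.** With no treatment effect, both tests reject in 4.9% to 5.2% of trials.

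**5. Chance imbalance.** With 45% GdE-positive, the 95% range of the difference between two arms is ±1.96 × √(2 × 0.45 × 0.55/333) = ±7.6 points. If lesion-free rates differ by 25 points between GdE groups (a strong effect, assumed), an imbalance at the edge of that range shifts the observed treatment difference by 0.076 × 25 = 1.9 points.

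**The case against.** The strongest reply is that nothing is wrong with the planned test. Its strata follow the Part B randomization factors, with region presumably a grouping of country, and that is a recognised basis for choosing them. Type I error is correct, and chance imbalance in GdE is ordinary random variation that the test already allows for. This stands, and it rules out any claim of bias. It is not a reason against the change, because the proposed strata keep region and EDSS.

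A reader might infer that the plan definitely gives up power, or that the loss is large. The documents do not support that. They give no lesion-free rates, no baseline GdE prevalence and no prognostic strength. A loss of about 9 points can be produced (55% against 64% power in 2,500 simulated trials with 332 per arm, 45% GdE-positive and a treatment odds ratio of 1.6). That requires control lesion-free rates of 90% and 50% in the two GdE groups, an odds ratio of (0.90/0.10)/(0.50/0.50) = 9. With 80% and 70%, an odds ratio of about 1.7, the same exercise shows no loss.

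Three further limits stand:

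- Both endpoints are outside the ranked key secondary testing, so no confirmatory claim rests on them.
- The comparison with the count models is loose. Those models use the number of GdE lesions and also age, and 13.6.4 describes the counts at Month 12 where the Synopsis and 8.2.1 say Month 24. The fix would narrow the difference in covariates without removing it.
- The Part B SAP may say more. A SAP can change such a test, as the Part A SAP did for its lesion-free endpoint. Until it is seen, the protocol's rule is the one on record.

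**Conclusion.** The point holds as a minor matter of efficiency and consistency. The planned CMH test is valid but leaves out a baseline value that all patients have and that the Part B count and relapse-rate models adjust for. Within the assumed range, adding it is worth essentially nothing for odds ratios up to 2, about 1 to 2 points of power at 3, and about 2 to 5 points at 5. If baseline GdE is not prognostic, it costs up to about 0.5 points. These sizes rest on assumed lesion-free rates, GdE prevalence and prognostic strength, on three regions, and on 333 evaluable patients per arm. They do not show that a loss will occur, only that the possible gain exceeds the possible cost.

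**What to change.** In protocol 13.6.4 and in the Part B SAP, stratify the CMH test for the two lesion-free endpoints by region, baseline EDSS category and baseline GdE lesions (absent, present). Alternatively, use logistic regression with treatment, region, EDSS category and baseline GdE, which avoids thin strata and comes closer to the protocol's own Part A model for the GdE-free proportion. If the sponsor prefers the present strata, a sentence giving the reason would do.

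The cost is one phrase in each document and no new assessments. The only statistical downside is the loss of up to about 0.5 points noted above.
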